STUDY TITLE:

**BIOMARKERS EVALUATION AND EFFECT OF MEPOLIZUMAB ON LOWER AND
UPPER AIRWAYS INFLAMMATION IN SEVERE REFRACTORY EOSINOPHILIC ASTHMA
AND NASAL POLYPOSIS**

NCT code:

05063981

Date last version:

12/09/2020

Type of study: Prospective Observational study

Partecipants:

PI: [name] **ICS Maugeri IRCCS Telese**
[name] and [name] **ICS Maugeri IRCCS Tradate**
[name] and [name] **ICS Mageri IRCCS Bari**
[name] **ICS Maugeri IRCCS Veruno**
[name] **CNR Pozzuoli Napoli**

Scientific rationale

Patients with severe or difficult-to-treat asthma represent a small amount of total asthmatic patients, but weight on the national health system for the costs of disease management. Chronic rhinosinusitis with nasal polyposis (CRSwNP) [1], which the Italian severe/uncontrolled asthma registry reported with a prevalence of 30% [2], represents a comorbidity that significantly impact lung function and asthma control in severe asthma [3]. Recent evidence indicates that there is a consistent heterogeneity regarding mucosal alterations present in subjects with nasal polyposis involving different pathways: inflammatory cells, remodeling, T cell activation, local IgE production, alteration induced by interactions between microorganisms and epithelial cells.

Hypothesis

Nasal, bronchial and systemic inflammation can differ among patients with severe refractory eosinophilic asthma with or without CRSwNP. Treatment with Mepolizumab could modify nasal, bronchial and systemic inflammation of patients with severe refractory eosinophilic asthma and nasal polyposis acting on disease control.

Objectives (or Research questions)

The aim of the study is to evaluate:

- differences in specific inflammatory pattern and metabolites between severe refractory asthma patients with or without nasal polyposis
- nasal, bronchial and systemic inflammation and metabolomics profile in patients with severe refractory eosinophilic asthma before and after treatment with Mepolizumab.

Study population

We will enroll 10 patients with severe refractory eosinophilic asthma plus CRSwNP and 10 patients with severe refractory eosinophilic asthma and no CRSwNP, for whom treatment with mepolizumab is indicated, according to the AIFA recommendations.

Inclusion criteria

- age >18 years
- diagnosis of severe refractory asthma according to the ERS/ATS criteria ATS
- Blood eosinophils >150 cells/mcL at the screening visit and at least one value of 300 or more eosinophils/mcL during the previous year;
- at least two exacerbations despite maximal therapy with long-acting bronchodilators and high dose inhaled corticosteroids in the previous year or the need for continued therapy with oral corticosteroids in addition to maximal inhaled therapy for at least 6 months in the previous year
- written informed consent.
- For CRSwNP diagnosis, the EPOS 2020 guidelines will be considered as reference.

All the above-mentioned inclusion criteria must be met.

Exclusion criteria

- Pregnancy
- Eosinophilic Granulomatosis with Polyangiitis (EGPA);
- Serious life threatening cardiopulmonary disorders;
- Systemic immunologic disorder in the last 12 months;
- Positive history for malignant tumors ever in patient's life;
- Immunodeficiency.

Study design and methods

Duration of the study.

The study will last 2 years. The enrollment period will last 1 year. The follow-up period will last 1 year. Visits and collection of biological fluids will be performed at baseline and at 6 and 12 months after initiation of treatment with Mepolizumab.

The following parameters will be evaluated

- Clinical history (age of asthma onset, duration of rhinosinusitis symptoms, ASA intolerance, number of asthma exacerbations in the previous year, ACT, ACQ, Morisky Medication Adherence Scale MMAS - 8, Lund-Mackay scores, treatment, etc.);
- Snot 22;
- Nasal polyps score;
- Visual analogue scale (VAS) for main symptoms of CRSwNP
- Lung function;
- Nasal endoscopy evaluation.

Nasal inflammation. Nasal cytology: cytopsin preparations for differential cell count of eosinophils, neutrophils, macrophages, T-cells. Nasal secretions by rhinowash: ELISA tests for identification and quantitation of IL-4, IL-5, IL-3, IL-13, IF γ , eotaxin (CCL11), TSLP GMCSF.

Bronchial inflammation. In induced sputum cytopsin preparations: differential cell count of eosinophils, neutrophils, macrophages, T-cells.

In bronchial sputum supernatants by ELISA tests: IL-4, IL-5, IL-3, IL-13, IF γ , eotaxin (CCL11), TSLP GMCSF.

In cytopsin preparations some selected receptors expressed by eosinophils, neutrophils or macrophages will be analyzed after evaluation of the prevalent secreted cytokines in the supernatants.

Systemic inflammation. Blood eosinophils and neutrophil count; serum specific IgE evaluation with microarray technology; ELISA tests for IL-4, IL-5, IL-3, IL-13, IF γ , eotaxin (CCL11), TSLP GMCSF.

Metabolomic analysis in exhaled breath condensate (EBC)

Pulmonary function tests. Flow rates will be determined using automated equipment (V Max 22 System Sensor Medics, Milan, Italy) according to ATS/ERS recommendations. Static lung volumes will be determined by the helium dilution method.

Nasal cytology. Nasal cytology will be assessed with nasal brushing. Nasal blown secretions will be collected by rhino-wash and processed as previously reported and supernatants stored at -80°C for soluble mediator evaluations [4].

Induced sputum. Sputum induction will be performed using a modification of the method suggested by prof. [name]. The supernatant will be stored at -80°C for soluble markers determination by high sensitive tests ELISA

Exhaled NO. Exhaled will be measured by an electrochemical analyzer (Hypair FeNO medisoft Exp'air, 2010) according to ATS-ERS recommendations for online measurement of FeNO in adults [5] and as previously shown [6].

Inflammatory markers. Blood will be withdrawn, percentage of blood eosinophils will be determined and serum and plasma stored at -20°C for soluble biomarkers determinations. IL-4, IL-5, IL-3, IL-13, IF γ , eotaxin (CCL11), TSLP GMCSF, will be evaluated in serum or plasma, induced sputum and nasal secretion supernatants with commercially available ELISA [7] .

Furhermore the Humanitas Laboratory under direction of prof. [name] will assess the following biological markers: Innate Lymphoid Cells 2 (ILC2) in sputum, Migration Stimulating Factor (MSF) Pentatraxin 3 (PTX3) Galectin 3 (GAL3) in plasma and sputum. Interleukina-5 (IL-5) in EBC.

EBC sampling. EBC will be collected with a TURBO-DECCS condenser set at -5.0 ± 1.0 °C (Medivac, Pilastrello, Parma, Italy, Medivac.it). Briefly, all subjects will be asked to breathe at tidal volume through the mouthpiece for 15 min while sitting comfortably and wearing a nose-clip. We will obtain, on average, 2.0 ± 0.3 ml (mean \pm SD) of EBC from each subject. EBC samples will be immediately sealed in polypropylene tubes and stored first in dry ice and then at -80°C until NMR acquisition [8].

The salivary contamination of the samples will be tested by measuring their α -amylase activity.

NMR-based metabolomics. Metabolomic analysis will be performed by NMR spectroscopy. 1D and 2D NMR spectra will be recorded at 27°C in a randomized sequential order on a 600-MHz Bruker Avance-III spectrometer equipped with a CryoProbe. Metabolites will be identified by resorting to 2D experiments and comparison with metabolite data banks.

Study Endpoints

The primary outcomes will be:

Evaluation of the differences in specific inflammatory pattern and metabolites between severe refractory asthma patients with or without nasal polyposis and correlation with clinical data.

Variation of specific inflammatory pattern and metabolites between severe asthmatic patients with or without nasal polyposis metabolites after treatment with Mepolizumab.

Statistical Plan

We will use multivariate analysis to discriminate signals/metabolites to identify hidden phenomena and trends in ensembles of NMR spectra. Subregions (buckets) of 0.02-ppm width of the spectra will be integrated using the AMIX 3.9.15 software (Bruker Biospin GmbH, Rheinstetten, Germany). Each bucket will be normalized to the total spectrum area, and the data matrix analyzed with multivariate statistical regressions. Principal Component Analysis (PCA) and Orthogonal Projection to Latent Structures Discriminant Analysis (OPLS-DA) will be carried out with the SIMCA P+14 package (Umetrics, Umeå, Sweden). PCA will first be applied to detect EBC metabolites trends and clusterings in an unsupervised (*i.e.*, no prior group knowledge is used in the calculation) manner, while OPLS-DA will be used to correlate the metabolic variations to pathophysiological changes.

We will also apply pathway topology and biomarker analysis on selected and more representative metabolites in class separation by resorting to MetaboAnalyst 4.0 software. Discriminating metabolites will be selected by evaluating both Variable Importance in Projection values greater than 1 in class discrimination and correlation values $|\rho|$ greater than 0.6.

Data will be reported as mean \pm standard deviation or median with interquartile range. Between-group comparisons will be performed by using Analysis of Variance (cross-sectional evaluation) and Analysis of Covariance (longitudinal study) with baseline values as covariates. Depending on the distribution of variable, the use of transformations or non parametric tests will be evaluated. Categorical variables will be reported as percentage and their associations will be analysed by chi-squared or Fisher exact test as appropriate. Because of the exploratory nature of the study, sample size is not formally computed but decided a priori. A p value of <0.05 will be considered statistically significant. The statistical analyses will be carried out using professional statistical software.

Pharmacovigilance

All adverse reactions encountered during the study for both the biological drug and the concomitant drugs will be reported to local pharmacovigilance officers, as required.

Limitations

Patients will be asked to return to the clinic with a frequency not much different to that of routine disease control to reduce possible drop out.

A possible problem could be the unsuitable sputum sample or patient with too compromised lung functions to undergo sputum induction function ($FEV_1 < 1.5L$). We will collect spontaneous sputum when available, while if the patient cannot expectorate or the induced sputum collected is not suitable (sample mainly constituted by saliva), FeNO measurement will be the surrogate evaluation for eosinophilic airway inflammation.

At the co-investigator unit, a specific asthma school is present in order to properly train severe asthmatic patients to manage the disease and to reduce non adherence. This approach will be useful to avoid drop-out and loss of adherence to the protocol.

References

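### Blood samples are to be kept at -20°C, while sputum and nasal fluid tested for the same mediators are kept at -80°C, with no reason given

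*Protocol*

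**What the plan says.** The methods text of the protocol contains four storage rules.

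- **Serum and plasma** (Inflammatory markers): "serum and plasma stored at -20°C for soluble biomarkers determinations".
- **Nasal secretions** (Nasal cytology): "supernatants stored at -80°C for soluble mediator evaluations".
- **Induced sputum** (Induced sputum): "The supernatant will be stored at -80°C for soluble markers determination by high sensitive tests ELISA".
- **Exhaled breath condensate** (EBC sampling): "stored first in dry ice and then at -80°C until NMR acquisition".

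The Inflammatory markers paragraph then names one panel (IL-4, IL-5, IL-3, IL-13, interferon gamma, eotaxin, TSLP and GM-CSF) that "will be evaluated in serum or plasma, induced sputum and nasal secretion supernatants with commercially available ELISA". A second laboratory is to measure "Migration Stimulating Factor (MSF) Pentatraxin 3 (PTX3) Galectin 3 (GAL3) in plasma and sputum".

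The second objective is to describe "nasal, bronchial and systemic inflammation and metabolomics profile in patients with severe refractory eosinophilic asthma before and after treatment with Mepolizumab". On timing, Duration of the study says: "Visits and collection of biological fluids will be performed at baseline and at 6 and 12 months after initiation of treatment with Mepolizumab". The protocol gives no reason for the different temperature in blood, no maximum storage time, and no statement of whether samples are assayed on arrival or in batches.

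**The concern.** The protocol's own standard for these analytes in airway fluid is -80°C. In blood they get a warmer rule with no explanation. The comparison that shows this is internal to the document and needs no outside stability data.

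Storage loss would matter because every patient receives mepolizumab, so no untreated group could reveal a drift due to storage alone. If a patient's three visits are assayed in one run, the baseline sample has been frozen longest. Any loss during storage lowers the baseline value most, so a later value looks higher by comparison. That creates an apparent rise on treatment or hides part of a real fall. A loss in the freezer cannot be recovered afterwards.

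**Working it through.** **1. The rules side by side**

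| Material | Temperature | Assayed for |
|---|---|---|
| Serum, plasma | -20°C | eight-mediator panel; MSF, PTX3 and GAL3 in plasma |
| Sputum supernatant | -80°C | eight-mediator panel (MSF, PTX3 and GAL3 are also measured in sputum) |
| Nasal supernatant | -80°C | eight-mediator panel |
| Breath condensate | dry ice, then -80°C | NMR metabolomics; IL-5 |

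The number of soluble mediators under the warmer rule in blood is 8 + 3 = 11. The last three count only if the single stated plasma rule also covers the plasma sent to the second laboratory, which the protocol does not say.

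**2. Age of the samples**

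Inputs from Duration of the study: one year of enrolment, one year of follow-up, sampling at 0, 6 and 12 months. Let a patient enter at month e, with e between 0 and 12, and suppose that everything is assayed at month 24 (an assumption).

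- Baseline sample: stored 24 - e months, that is 12 to 24.
- 12-month sample: stored 24 - (e + 12) = 12 - e months, that is 0 to 12.
- Difference within a patient: (24 - e) - (12 - e) = 12 months, whatever the entry date.

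The 12-month difference arises whenever a patient's visits are assayed together. If each sample is assayed on arrival, it is about zero. Visit windows are not stated, so 12 months is approximate.

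**3. Effect on a before/after ratio**

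Let L be the extra share of the mediator that the baseline sample loses relative to the 12-month sample. The protocol gives no value, so L is assumed at 0, 0.05, 0.10 and 0.20.

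- With no true change, the apparent change is 1/(1 - L) - 1.
- With a true fall f, the apparent change is (1 - f)/(1 - L) - 1. It is zero when L = f.
- If -80°C halved the loss (assumed), the apparent change with no true change is 1/(1 - L/2) - 1.

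| Assumed L | False rise, no true change | True 20% fall reads as | False rise if the loss is halved |
|---|---|---|---|
| 0% | 0% | -20% | 0% |
| 5% | 1/0.95 - 1 = 5.3% | 0.8/0.95 - 1 = -15.8% | 1/0.975 - 1 = 2.6% |
| 10% | 1/0.90 - 1 = 11.1% | 0.8/0.90 - 1 = -11.1% | 1/0.95 - 1 = 5.3% |
| 20% | 1/0.80 - 1 = 25.0% | 0.8/0.80 - 1 = 0% | 1/0.90 - 1 = 11.1% |

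If -80°C made no difference to the loss, the last column would equal the second.

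**4. Which results are exposed**

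Both primary outcomes under Study Endpoints compare patients with and without nasal polyposis. The Statistical Plan uses analysis of variance across groups and analysis of covariance on baseline. Both groups' blood is stored at the same temperature and sampled on the same schedule, so a common loss falls on both alike and these comparisons are largely unaffected. Blood eosinophil and neutrophil counts are not measured on stored serum or plasma. That leaves the before/after reading of stored blood mediators in the second objective.

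**The case against.** The strongest reply is that nothing here conflicts. Each material has one temperature, and different materials may reasonably have different rules. Harm needs three things that the protocol does not establish: that these mediators degrade at -20°C over the storage period, that they degrade less at -80°C, and that a patient's visits are assayed together. If any one fails, the change gains nothing, and the loss values in the table are chosen, not observed. The remedy also does not address the mechanism directly. The bias comes from unequal sample age, which colder storage does not remove and which applies equally to sputum and nasal fluid. Finally, the exposed result is narrow: the Statistical Plan names no within-patient test for it, and the study is described as exploratory, with 20 patients.

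Most of this stands. It is a design choice and not a contradiction, the size of any loss is unknown and may be zero, and the between-group results are largely safe. The breath condensate is also weak support, since it is kept mainly for NMR and shares only IL-5 with the panel.

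What does not follow is that the point should be dropped. The protocol itself fixes the temperature, so this is not a detail left to another document. It sets a stricter rule for the same analytes in sputum and nasal fluid. It leaves open the batch timing under which the problem would arise, and the before/after evaluation of systemic inflammation is a stated aim.

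**Conclusion.** The point holds as a minor, low-cost improvement. The protocol applies a warmer rule to up to 11 mediators in blood than to the same mediators in airway fluid, and does not say why.

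The possible consequence is a bias towards a rise in the before/after blood results. It depends on two assumptions: that a patient's visits are assayed together, and that some loss occurs in storage. Over the assumed range of 0% to 20% extra loss at baseline, the false rise runs from 0% to 25.0%. A true 20% fall is fully hidden only at the top of that range. These figures show scale and are not evidence that a loss exists. The benefit of -80°C likewise cannot be quantified from the protocol.

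**What to change.** In the Inflammatory markers paragraph, change the serum and plasma temperature to -80°C, as already required for the sputum, nasal and breath condensate samples. State that the rule also covers the plasma for MSF, PTX3 and GAL3. Record the freezing and assay dates of each sample, so that storage time is known and the before/after blood results can be checked against it. If -20°C is deliberate, give the reason in one sentence instead and still record the dates.

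The colder temperature is meant to limit the size of any loss. The age difference between visits remains, in blood as in the other fluids, which is why the dates are needed.

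The cost is one temperature in one sentence, the dates in the sample log, and some -80°C freezer space for 20 patients × 3 visits = 60 blood collections. Storage at -80°C is already required for the other fluids.

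### For the before/after metabolomic comparison in the same 20 patients, the protocol names ordinary OPLS-DA as its only supervised method and no within-patient analysis, which gives away sensitivity

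*Protocol*

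**What the plan says.** The second item under Objectives is to evaluate "nasal, bronchial and systemic inflammation and metabolomics profile in patients with severe refractory eosinophilic asthma before and after treatment with Mepolizumab". This compares each patient with himself or herself. Under Duration of the study, "Visits and collection of biological fluids will be performed at baseline and at 6 and 12 months after initiation of treatment with Mepolizumab". Under Study population, "We will enroll 10 patients with severe refractory eosinophilic asthma plus CRSwNP and 10 patients with severe refractory eosinophilic asthma and no CRSwNP". That makes 20 patients and, at three visits each, up to 60 spectra.

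The Statistical Plan fixes the handling of the spectra in some detail: bucket width, normalisation to total area, and software with its release. PCA is the unsupervised step, and then "OPLS-DA will be used to correlate the metabolic variations to pathophysiological changes". The selection rule begins "Discriminating metabolites will be selected by evaluating both Variable Importance in Projection values greater than 1 in class discrimination and correlation values", with an absolute correlation cut-off of 0.6. Pathway and biomarker analysis follows on the more representative metabolites.

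For between-group comparisons generally, the plan adds ANOVA for the cross-sectional evaluation and "Analysis of Covariance (longitudinal study) with baseline values as covariates". The second primary outcome is worded between groups: "Variation of specific inflammatory pattern and metabolites between severe asthmatic patients with or without nasal polyposis metabolites after treatment with Mepolizumab". No within-patient before/after method is named for any variable. The plan does not say which classes enter OPLS-DA (polyposis group, visit or both), or how its cross-validation folds are formed.

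**The concern.** Ordinary OPLS-DA takes every spectrum as a separate member of a class. If the classes are before and after, it does not know that a given pair of spectra comes from one person. Patients differ from one another in ways that persist across visits, and that variation obscures the treatment change, although subtracting each patient's own level would remove it. With only 20 patients, pairing is a main source of precision and costs nothing to use.

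The metabolomic profile is one of four items in the second objective, and metabolites appear in both primary outcomes. The multivariate step also decides which metabolites go forward to pathway and biomarker analysis. A metabolite missed there would not be examined in that later step.

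**Working it through.** **Inputs from the protocol.** 20 patients; visits at 0, 6 and 12 months; groups of 10 and 10; "A p value of <0.05 will be considered statistically significant" (sidedness not stated, two-sided assumed). There is no power figure to reproduce, since the sample size was not formally computed.

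**Assumed inputs.** Total SD of one bucket = 1; before/after change 0.6 SD (0.5 SD as a second case); within-patient correlation r = 0.3, 0.5, 0.7. The t-tests below only gauge the value of pairing; the protocol does not plan them for the buckets.

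**Step 1, standard error of the change, n = 20.**
- Pairing ignored: sqrt(2/20) = 0.316.
- Pairing used: sqrt(2(1 − r)/20) = 0.265, 0.224, 0.173 for r = 0.3, 0.5, 0.7.
- Ratio 1/sqrt(1 − r) = 1.20, 1.41, 1.83.

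**Step 2, power per bucket.** Paired power comes from the noncentral t with 19 df. For 0.6 SD the noncentrality is 0.6/0.265 = 2.27, 0.6/0.224 = 2.68 and 0.6/0.173 = 3.46. The unpaired columns are simulated (100,000 runs).

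| r | Unpaired, 0.6 SD | Paired, 0.6 SD | Unpaired, 0.5 SD | Paired, 0.5 SD | Unpaired rejection, no change |
|---|---|---|---|---|---|
| 0.3 | 45% | 58% | 31% | 43% | 2.1% |
| 0.5 | 44% | 72% | 29% | 56–57% | 0.7% |
| 0.7 | 43% | 91% | 25% | 78% | 0.1% |

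The last column is below the nominal 5%, so ignoring the pairing is conservative for before versus after.

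**Step 3, the same question with a multivariate classifier.** A one-component PLS-DA stood in for OPLS-DA (20 patients × 2 visits, 400 independent buckets, 20 of them changed by 0.5 SD, whole patients left out). Mean cross-validated Q²:

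| r | Ordinary | Multilevel (patient mean subtracted) |
|---|---|---|
| 0.3 | 0.15 | 0.22 |
| 0.5 | 0.19 | 0.30 |
| 0.7 | 0.25 | 0.44 |

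The ordinary model still finds a signal, but a weaker one. If single spectra are left out instead, its mean Q² turns negative (−0.57, −1.46, −3.32). The fold rule therefore matters as well.

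**Step 4, a conditional case.** Suppose all three visits were pooled as independent spectra for the polyp contrast, 30 against 30, with no true group difference. The variance of a group mean would be understated by 1 + 2r = 1.6, 2.0, 2.4. Simulated type I error at nominal 5% is 12%, 17% and 22% for r = 0.3, 0.5, 0.7. The protocol does not say that visits are pooled.

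**The case against.** The strongest reply is that naming OPLS-DA does not commit the sponsor to an unpaired version. The protocol does not say that visits are the classes, the quoted sentence could accommodate change data, and multilevel OPLS-DA is the same algorithm on centred input. Input coding, fold rule and permutation scheme could sit in a SAP that is not available here. This stands in part: the missing fold rule alone would be no finding. But the protocol already descends to software release and selection cut-offs, and within that detail it names the method without anything that uses the pairing its second objective depends on.

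The ANCOVA is also a fair answer to part of the question. It is not restricted to non-NMR variables, it uses each patient's baseline, and it serves the second primary outcome as worded, which contrasts the two polyposis groups. It does not address the overall before/after change in the second objective, and it leaves the multivariate selection step as it is.

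A reader might infer that the paired change is being tested against the wrong error term. The documents do not support that: the VIP and correlation cut-offs are a selection rule, not a test. A reader might also infer that the plan would produce a spurious polyp signature. That needs visits to be pooled, which is stated nowhere; the plan's separation of cross-sectional from longitudinal evaluation points the other way.

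Finally, the study is observational and declared exploratory, and at r = 0.3 the gain from pairing is modest.

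**Conclusion.** The point holds in a limited form. OPLS-DA is the only supervised method named for the spectra, no within-patient analysis is named, and the ANCOVA covers only the between-group contrast. If OPLS-DA is run in its ordinary form on before and after spectra, the cost is lost sensitivity: for an assumed 0.6 SD change, about 44% power per bucket instead of 58% to 91%. It creates no excess of false positives in that comparison. The 12% to 22% type I error applies only if visits were pooled for the polyp contrast.

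Every magnitude rests on an assumed change, SD and within-patient correlation, and on t-tests or PLS-DA standing in for OPLS-DA with its cut-offs. They show direction and rough scale. For an exploratory study this is a cheap improvement of moderate importance, held with medium confidence.

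**What to change.** Add to the Statistical Plan:

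- **Before versus after mepolizumab:** use multilevel OPLS-DA (each patient's own mean subtracted) or OPLS on within-patient differences. In cross-validation leave out all spectra of a patient together, and in permutation tests permute the visit labels within patient.
- **With versus without CRSwNP:** use one spectrum per patient per model, or keep all spectra of a patient in the same fold and permute the group labels by patient.

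The same samples and spectra serve, and no further visits are needed. The one small cost is that a patient with only one usable spectrum drops out of the paired model; that patient can still contribute to the group comparison.

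### With 10 patients per group, the fixed rule for naming discriminating metabolites (VIP above 1 and |rho| above 0.6, rho undefined) does not reliably separate signal from noise

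*Protocol*

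**What the plan says.** The protocol's Study population section fixes the groups: "We will enroll 10 patients with severe refractory eosinophilic asthma plus CRSwNP and 10 patients with severe refractory eosinophilic asthma and no CRSwNP". Under Study Endpoints, the first primary outcome includes this contrast: "Evaluation of the differences in specific inflammatory pattern and metabolites between severe refractory asthma patients with or without nasal polyposis".

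The Statistical Plan describes the metabolomic analysis in four steps:

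- Variables: "Subregions (buckets) of 0.02-ppm width of the spectra will be integrated". Neither the spectral range nor the number of buckets is given.
- Model: PCA first, then "OPLS-DA will be used to correlate the metabolic variations to pathophysiological changes".
- Selection: "Discriminating metabolites will be selected by evaluating both Variable Importance in Projection values greater than 1 in class discrimination and correlation values" with absolute rho greater than 0.6. Both conditions must hold. Rho is not defined.
- Use: the authors will "apply pathway topology and biomarker analysis on selected and more representative metabolites in class separation".

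The same section assigns cross-sectional group comparisons to analysis of variance and longitudinal ones to "Analysis of Covariance (longitudinal study) with baseline values as covariates". On size it says: "Because of the exploratory nature of the study, sample size is not formally computed but decided a priori".

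**The concern.** The protocol does not leave selection open. It states two numeric cut-offs and calls whatever passes them discriminating, for a contrast that belongs to a primary outcome. With 20 patients and possibly hundreds of buckets, cut-offs of this kind can produce a short list from noise alone, and a reader of the final report could not tell whether the list exceeds chance. The undefined rho adds to this, because two analysts following the same text could name different metabolites. The selected set then goes into biomarker analysis and no second cohort is named, so a performance figure on that set would reuse the patients who chose it.

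**Working it through.** The plan gives no error rate, power or accuracy to reproduce.

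**Inputs from the protocol.** 10 + 10 patients; VIP > 1; |rho| > 0.6; 0.02-ppm buckets.

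**Assumptions.** The bucket count is taken as 200 to 450, with smaller numbers also tried. Rho is read in two ways: correlation of a bucket with class, or with the OPLS-DA predictive score.

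**Step 1: VIP > 1.** Squared VIPs average 1 by construction. With unit-variance scaling and one predictive component, the weight of a bucket is proportional to its correlation r with class, so VIP is |r| divided by the root mean square of r. On noise that root mean square is about 1/√(n−1) = 1/√19 = 0.229. VIP > 1 therefore means roughly |r| > 0.23. This is t = 0.229·√(18/(1−0.0526)) = 1.00, with a two-sided tail on 18 df of 0.33. Simulation gave 24 to 34% across scalings and correlation structures. A bucket at |r| = 0.6 has VIP of about 0.6/0.229 = 2.6, so the VIP condition removes almost nothing that the correlation limit keeps.

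**Step 2: |r| > 0.6 with class.** t = r·√((n−2)/(1−r²)) = 0.6·√(18/0.64) = 3.18, p = 0.0052 per bucket. For m independent noise buckets the expected number passing is 0.0052·m, and the chance of at least one is 1 − (1 − 0.0052)^m:

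| m | expected | at least one |
|---|---|---|
| 100 | 0.52 | 40% |
| 200 | 1.03 | 64% |
| 400 | 2.07 | 87% |
| 450 | 2.32 | 90% |

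**Step 3: the full rule on noise.** Real buckets are correlated and normalised to total area, so the rule was simulated.

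- *Simulation A:* log-normal intensities, total-area normalisation, 1 or 2 orthogonal components, unit-variance or Pareto scaling, 1000 datasets per setting. Buckets were independent, in blocks of 4, or driven by 40 latent metabolites. For 200 to 450 buckets, at least one was named in 36 to 82% of datasets (class; mean 0.6 to 1.7 buckets) or 42 to 82% (score; mean 0.7 to 2.7). With 20 to 60 independent variables it was 7 to 19% (class) or 21 to 64% (score).
- *Simulation B:* autoscaled data, 300 datasets per setting, other correlation structures. For 200 to 400 buckets it gave 48 to 85% (class) and 66 to 86% (score).

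**Step 4: the two readings of rho.** With 40 latent metabolites, the class and score readings gave different lists in 20 to 69% of simulated null studies.

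**Step 5: when real differences exist.** If 10 of 400 independent buckets truly differ by 1.0 SD, each passes |r| > 0.6 with probability 0.213. That gives 2.13 true and 390·0.00516 = 2.01 false buckets, a false share of 2.01/4.14 = 49%. The share is 63% at 0.8 SD and 26% at 1.5 SD. Simulation A, with 300 buckets, gave 20 to 49% noise among named buckets.

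**Step 6: performance on the selected set.** On noise, in datasets that named at least one bucket, apparent AUC was 0.87 to 0.92 (A), against 0.55 to 0.62 with selection repeated inside patient-level folds. In B, apparent accuracy was 0.80 to 0.89. Leave-one-out with selection done once on all 20 patients still gave 0.79 to 0.87; with selection repeated in each fold it gave 0.44 to 0.53, where chance is 0.50.

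**Step 7: the before/after contrast.** For a pooled comparison of 20 before with 20 after, the naming rate was 0 to 3% (score) or 0% (class) with within-patient correlation 0.5, and 0 to 11% or 0 to 2% with correlation 0. The concern there is small.

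**The case against.** **The rule does filter.** A reader might infer that it cannot tell signal from noise at all. The figures do not support that. The joint rule passes under 1% of noise buckets; if rho is correlation with class, it is about ten times stricter per bucket than p < 0.05; and in Simulation A 51 to 80% of named buckets were real when real differences existed. What fails is reliability over many buckets.

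**The study is exploratory.** The protocol says so, and chance hits are acceptable as leads. This stands and lowers the severity. It does not remove the point, because the rule labels its output discriminating within a primary outcome and gives no means of judging whether the list exceeds chance.

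**No accuracy measure is planned.** A reader might infer that the protocol intends to report an inflated AUC. It names neither accuracy nor AUC, only biomarker analysis of the selected set, so the optimism is conditional on such a figure being computed.

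**Validation may be in a SAP.** This also stands: silence on cross-validation or permutation is not the finding. The finding is what the stated rule does, and that one of its two terms is undefined.

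**The size rests on assumptions.** Bucket count, correlation structure, scaling and number of components were all assumed, and the results run from 7% to 86%. A third reading, rho as correlation with a clinical variable, was not tested, and the figures do not apply to it.

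**Analysis of variance is also named.** It is assigned to cross-sectional comparisons, so OPLS-DA is not clearly the only basis for the primary contrast. Running it on the same 20 patients would not correct the selection.

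**Conclusion.** The point holds for the 10-versus-10 contrast of the first primary outcome, as a minor to moderate one. As stated, the rule will often name at least one metabolite bucket when there is no difference: roughly 40 to 80% of studies if there are 200 to 450 buckets, and clearly less often if the effective number of variables is only 20 to 60. The two tested readings of rho often give different lists, so the rule is not reproducible from the text. If a performance measure is computed on the selected set in these patients without repeating the selection, about 0.9 apparent AUC is to be expected from noise. The point does not extend to the longitudinal between-group comparisons, which the protocol assigns to analysis of covariance.

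**What to change.** In the Statistical Plan:

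1. State what rho is correlated with.
2. Report, beside the selected list, a label-permutation p value for the whole procedure, refitting the model and reselecting in every permutation.
3. Where that p value is not below 0.05, keep the list and any pathway analysis, but label it hypothesis-generating and not discriminating.
4. If any accuracy or AUC is reported, repeat the VIP and |rho| selection inside patient-level cross-validation folds, with all visits of a patient in one fold, and give the estimate with its uncertainty.

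The cost is a few sentences and some computing; no patient, visit or assay changes. Performance figures will look less favourable and, with so few patients per fold, imprecise. The permutation test has low power here: in Simulation A its p value was below 0.05 in 10 to 50% of datasets when 2 to 4 of 40 metabolites differed by 1.0 to 1.5 SD, and in 21 to 71% when 10 of 300 independent buckets differed, against 3 to 6% with no difference. For that reason it should decide the label and not delete the list.
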